#### OUTCOME MEASURES for each AIM:

Aim 1: Evaluate therapeutic and neuroplastic effects of myoelectric upper limb orthosis

When assessing robot- or orthosis-assisted functional tasks, no one measure is perfectly applicable [34], hence we will use a combination of outcome measures. To evaluate the therapeutic effect of the myoelectric upper limb orthosis with powered elbow and grasp, outcome measures will include range of motion, MAS, the Wrist Position Sense Test, monofilament test of sensation, and the Fugl-Meyer Assessment of Motor Recovery upper limb subsection. These measures will be performed without the orthosis to assess whether therapy/training combined with device usage result in carry-over effects at the body structure level over time. See Table 2 for overview of schedule of assessments.

Passive range of motion is the amount of motion of a joint measured in degrees by a clinician with a goniometer during a passive movement. Passive range of motion of the elbow and fingers will be assessed.

The MAS will be used to assess muscle tone and spasticity [17]. Using a 5 point scale, the clinician evaluates resistance to passive movement about a joint with varying degrees of velocity. The MAS has been widely used to quantify muscle tone following brain injury. Interrater reliability of MAS for arm assessments has been reported as kappa=0.92 or percent of agreement = 97.4% [35].

The Wrist Position Sense Test is a somatosensory test that measures a person's ability to recreate a wrist position without vision; muscle, joint and tendon receptors that guide the movement using a purpose built proprioception apparatus [36]. For example, for measuring proprioception at the wrist joint, the hand is placed in a splint with the thumb up and the forearm is secured in a neutral position in a splint on the table in front of the proprioception apparatus which is housed in the lab of our Cleveland VA site-PI (the Brain Plasticity and NeuroRecovery Research Lab of the Cleveland FES Center). The examiner tests discrimination accuracy at 20 different predetermined wrist positions. With vision occluded by a curtain, subjects are asked to estimate wrist position using a response pointer. The score is calculated as an average of absolute error between actual and response positions in degrees. This test has test-retest reliability of about 0.9 in stroke patients [36]. The same test can also be used to assess elbow and wrist proprioception. Semmes-Weinstein Monofilaments provide a non-invasive evaluation of cutaneous sensation levels throughout the body. Testing will be done in a quiet area of [name] lab to help the subject fully attend to the testing procedure. The subject's upper limb will be rested on a stable, padded surface and their vision occluded by using a shield or by having the subject look away. The testing procedure will be explained to the subject and the subject instructed to respond when the stimulus is felt by saying "yes". Testing will proceed from distal to proximal and from small to large monofilaments. We will test different areas of the arm innervated by different nerves. For example, we will test the palmar surface of the index finger and thumb to evaluate the median nerve; the little finger and hypothenar eminence to evaluate the ulnar nerve; and the dorsum of the hand to evaluate the radial nerve. The filament will be pressed at a 90° angle against the skin until it bows, held in place for 1.5 seconds, and then removed. This is repeated up to three times. A consistent localization of the smallest filament is recorded as a score at a given site. For screening, if the subject responds to the stimulus in all sites, normal cutaneous sensation will be recorded and the examination considered complete. If the subject does not respond to the stimulus, the next largest monofilament will be used and the process repeated. For scoring as an outcome measure, we will add up the score based on the smallest monofilament size localized. In other words, monofilament score is a sum of the smallest filament sizes

localized at each testing site. For example, when testing 5 sites the smallest or the best screen is equal to  $1.65 \times 5$ .

The Fugl-Meyer Assessment of Motor Recovery upper limb subsection is one of the most widely used quantitative measures of motor impairment [37]. The upper limb subsection includes 33 items measuring movement, coordination, and reflex action about the shoulder, elbow, forearm, and wrist with a three-point scale from zero (unable to perform) to two (able to perform) used to score each item for a total score of 66. It has good intrarater (ICC = 0.99) and interrater (ICC = 0.96) reliability for use with stroke patients [38] and TBI patients (ICC = 0.97) [39].

#### Neuroplasticity measures.

**H Reflex.** Stimulation of a peripheral nerve (median nerve in our study) will evoke a compound muscle potential (M wave in the flexor carpi radialis muscle) and an H wave (H-reflex;[63]). We will evaluate and compare the H/M ratio at specific points along the course of the study. A higher H/M amplitude ratio is associated with enhanced spinal excitability and a mitigation of spasticity is correlated with a reduction of H/M ratio [64].

MRI and TMS neuroplasticity measures (described below) will be collected for study participant who meet TMS and MRI inclusion/exclusion safety criteria (Item#30). If subjects do not meet the TMS and MRI inclusion/exclusion safety criteria, these measures will not be collected.

MRI. In order to identify the changes in neuronal networks following device use, we will obtain an MRI before and after treatment. MRI will be obtained in the MRI suite of the Cleveland VA by a trained technologist using manufacture pre-programmed protocols. Changes in MRI-based measures will be analyzed by our laboratory to determine if any structural or functional changes have occurred as a result of device use. MRI will be performed during a separate visit from the rest of the outcome measures data collection.

#### Single-pulse TMS-induced measures.

Motor Evoked Potential recruitment curve (MEP-rc). We will use a Magstim 2002 transcranial magnetic stimulator (Magstim Company Ltd., Wales, UK). While patients are seated, a TMS coil will be placed tangential to the skull in the anterior posterior direction. The location of targets for stimulation will be guided using frameless stereotactic navigation (Brainsight2, Rogue Research, Inc., Montreal, QC). Surface electromyographic (EMG) electrodes will be placed over the bellies and tendons of the contralateral first dorsal interosseous muscle, extensor carpi radialis and flexor carpi radialis. EMG will record Motor Evoked Potentials (MEPs) in response to TMS of primary motor area, M1. The optimal site for each muscle in the contralateral M1 will be identified as the 'hotspot'[59]. The hotspot will be defined as the site that evokes  $50\mu V$  MEPs, using the lowest TMS intensity (resting motor threshold, rMT), in the contralateral muscle reliably in 6 out of 10 trials. Active motor threshold (aMT) will be determined as a lowest stimulator output to produce  $200\mu V$  MEP in 6 out of 10 trials while the subject activates a targeted muscle at 20% of maximum voluntary contraction, monitored with visual feedback of the EMG recording.

After determining the 'hot spot' location, we will obtain MEP-rc. MEP-rc will be generated first dorsal interosseous muscle, extensor carpi radialis and flexor carpi radialis of the paretic and non-paretic upper limb. Resting and active MEPs will be recorded with EMG skin adhesive

electrodes placed over muscles' bellies. Single-pulse TMS will be applied at the hotspot. The evoked MEPs will be recorded at stimulator intensities between 50% and 150% of. The mean MEP peak-to-peak amplitude is plotted against SO creating the recruitment curve MEP-rc. The area under the MEP-rc curve is the cortical excitability outcome measure[60]. The range of stimuli recorded will be determined for each subject separately, and held constant at each recording session to compensate for the more variable nature of the stroke-affected MEP response[61]. The EMG electrodes positions will also be replicated between sessions. The area under MEP-rc captures the cortical excitability changes while controlling for TMS and EMG recording variables.

Ipsilateral silent period (iSP). In order to evaluate transcallosal inhibition, we will analyze the iSP in the flexor dorsal interosseous muscle. An iSP in the affected limb is elicited by stimulating the M1 hotspot of the unaffected muscle while the paretic muscle is active. The reduction in muscle activity due to the ipsilateral stimulation is analyzed. Suprathreshold TMS is applied at 150% of the unaffected muscle's rMT (or at 100% SO, in the event of high rMT) while the subject activates their affected muscle at 20% of their maximum voluntary contraction level, monitored with visual feedback of the EMG recording. The EMG data from 10 stimuli are recorded, averaged and rectified. The iSP onset and offset are determined by analyzing the averaged, rectified data relative to a threshold determined by the pre-stimulus mean EMG value. iSP onset is defined as when the EMG falls below the threshold, and iSP offset is when the EMG returns to within 25% of the threshold for at least 50 ms[62]. We will compute both duration and the amount of EMG suppression during iSP.

Aim 2: Evaluate functional effects of myoelectric upper limb orthosis

To evaluate the functional effect of the myoelectric upper limb orthosis with powered elbow and grasp, outcome measures will include performance-based measures such as the Box and Block Test (BBT) and the Chedoke Arm and Hand Activity Inventory (CAHAI). The performance-based measures will be performed both with and without the orthosis to assess whether device usage improves function at the level of activity over time. During the period of home use, patient reported measures such as the Orthotic and Prosthetic Users' Survey (OPUS) upper extremity functional status (OPUS-UEFS) and satisfaction with device (OPUS-Sat) as well as the Revised Craig Handicap Assessment and Reporting Technique (CHART) to assess life-role participation and level of community integration will be added. The patient-reported measures will be completed to assess whether device usage at home improves perception of function and participation over time. See Table 2 for overview of schedule of assessments.

The Box and Block Test (BBT) is a standardized assessment of unilateral gross manual dexterity.

Individuals are seated at a table, facing a rectangular box that is divided into two square compartments of equal dimension by means of a partition. One hundred and fifty colored, wooden 2.5cm blocks are placed in one of the compartments. The individual is instructed to move as many blocks as possible, one at a time, from one compartment to the other for a period of one minute. Standardized dimensions for the test materials and procedures for test administration and scoring have been described [40]. To administer the test, the examiner is seated opposite the individual in order to observe test performance. The BBT is scored by counting the number of blocks carried over the partition during the one-minute trial period. Subject's hand must cross over the partition in order for a point to be given, and blocks that drop

or bounce out of the second compartment onto the floor are still rewarded with a point. Multiple blocks carried over at the same time count as a single point. Higher scores on this test indicate better gross manual dexterity. Psychometric properties have tested well in numerous populations including TBI [39].

Performance of ADLs will be assessed using the Chedoke Arm and Hand Activity Inventory (CAHAI), which is suitable for populations with upper limb paresis [41]. This test consists of 13 functional tasks (open jar of coffee, call 911, draw a line with a ruler, put toothpaste on toothbrush, cut medium consistency putty, pour a glass of water, wring out washcloth, clean pair of eyeglasses, zip up a zipper, do up five buttons, dry back with towel, place container on table, carry bag upstairs). It is not designed to measure the subject's ability to complete the task using only their unaffected hand, but rather to encourage bilateral function.

Patient's perception of function and satisfaction with the myoelectric arm orthosis will be assessed using the OPUS. The OPUS is a set of self-report instruments that assess functional status, quality of life, and satisfaction with device and service in persons who use orthoses and prostheses [42]. The original OPUS-UEFS was composed of 14 bilateral and 9 unilateral activities. Examples include drinking from a paper cup, buttoning a shirt, and tying shoelaces. The five-point rating scale ranges from "cannot perform" to "very easy." Jarl et al. [43] evaluated six additional items in a sample of 134 upper limb orthosis and prosthesis users. The new items included taking bank notes from a wallet, twisting a lid off a small bottle, and sharpening a pencil. One original item misfit and one new item demonstrated a high residual correlation. The resulting 27-item scale showed excellent reliability for orthosis users. For the OPUS satisfaction with device 12-item set [42], the easiest items to endorse are "the weight of my prosthesis (or orthosis) is manageable" and "my prosthesis (or orthosis) is durable." Items of average difficulty were "it is easy to put on my prosthesis (or orthosis)" and "my clothes are free of wear and tear from my prosthesis (or orthosis)." The most difficult items to endorse are "my skin is free of abrasions and irritations" and "my prosthesis (or orthosis) is pain free to wear." A recent literature review suggested that the OPUS is the only measure available to assess satisfaction with devices in orthosis users [44]. The OPUS uses Likert scale responses for each item of each module. However, these responses can be converted into a single score for each module for analysis[45-48].

The Revised Craig Handicap Assessment and Reporting Technique (CHART) is a questionnaire designed to identify the extent of life-role participation and level of community integration [49]. It is a 32-question instrument with life role domains pertaining to cognition, physical and financial independence, mobility, occupation, and social integration. The CHART is a stable and reliable measure for a variety of diseases and impairments and has been tested in SCI, TBI, multiple sclerosis and stroke [50,51,52].

Clinical assessments will be performed by PI, therapist and study staff.

Table 2 Schedule of Assessments

	Part 1: Enrollment			Part 3: 7	Therapy	Part 4: Home Use				
Assessment	Screen	Week 1 (Baseline)	Wk 5	Wk 7	Wk 9	Wk 11	Wk 13	Wk 16	Wk 19	Wk 22
	X	assessed with	out orth	osis; O	assesse	d with or	thosis			
Passive ROM	X	X	X	X	X	X	X	X	X	X
Active shoulder ROM	X		X	X	X	X	X	X	X	X

MMT	X		X				X	X	X	X
EMG signal	X		X				X	X	X	X
MAS	X	X	X	X	X	X	X	X	X	X
Read English	X									
Shoulder subluxation, pain, dislocation Skin rash/open wounds	X	Ongoing r subluxation such as addir	would r	esult in	subject w ness was	vithdrawa	al from t	he study	if modif	ications
Monofilament	X	X	X		X		X	X		X
		Per	forman	ce-Base	l Measu	res				
Wrist Position Sense Test		X	X		X		X	X		X
Fugl-Meyer		X	XO	XO	XO		XO	XO	XO	XO
BBT		X	XO		XO		XO	XO	XO	XO
CAHAI		X	XO		XO		XO	XO	XO	XO
		Pa	tient-Re	eported	Measure	es				
OPUS-UEFS		X					X			X
OPUS-Sat		X					X			X
CHART		X					X			X
MRI		X					X			
TMS (MEP-rc/iSP		X			X		X			X
H-reflex		X			X		X			X

14. Will the research involve the following?

	□ N/A Chart/Dat	a Keview	
	Placebo Group	⊠ No	☐ Yes (describe):
	Other Control Group	p 🛮 No	Yes (describe):
	Randomization	⊠ No	Yes (describe):
	Deception	⊠ No	Yes (describe):
	Information in any fo ☐ No ☐ Yes	orm or mediun  If yes, com	nd/or disclosure of Individually Identifiable Health n?  uplete the required HIPAA Waiver/Authorization forms.  ration of a study agent that does not require FDA approval
. 0.	v		itamins, food supplements, isotope tracers, alternative
	⊠ No ☐ Yes	s -provide a deta	ailed description of the procedures used to assure patient safety:

17.	Will radioactive material be administered or will subjects be exposed to ionizing radiation?
	
 
Ex. Radiographic equipment, fluoroscopic equipment, and CT scanners, etc.
 
No ☐ Yes
 

18.	In your judgment, could the objectives of the research be met in a way that presents less risk to subjects?
	No ☐ Yes please explain:
	Section 4 – Subject Selection, Recruitment, and Vulnerable Populations
19.	Anticipated duration of entire study reported in years: 6 years or till July 2022
20.	Estimated number of subjects to be studied at the LSCDVAMC or charts/records to be reviewed.
	• Provide answers for each cohort including normal controls; (patients, family members, treating physicians,):
	70 TBI or stroke subjects to enroll 20
21.	Estimated number of subjects to be studied or charts/records to be reviewed at all sites
	
 
Provide answers for each cohort including normal controls; (patients, family members, treating physicians,)
 

	N/A SINGLE SITE
22.	Duration of individual subject participation
	Provide answers for each cohort including normal controls; (patients, family members, treating physicians,). 31 study related visits (over approximately 22 weeks)
	Chart/record review N/A
23.	Age range of subjects
	• provide answers for each cohort , including normal controls:
	☐ Specific age range (list age range):
	☐ Children –waiver from VACO: ☐ attached ☐ pending- provide submission date:
	**Contact AO/Research [contact] for guidance
24.	Which of the following will be recruited or reviewed for this study (check all that apply)?
	☐ Veteran Inpatients

☐ Veteran Families
*Normal volunteers
*Non-Veterans; Provide justification If we are unable to recruit sufficient Veterans within our LSCDVAMC population that meet the study selection criteria and allow us to keep pace with the target enrollment rate, we will recruit subjects from the non-VA community. Our Cleveland VA site-PI, has experience recruiting non-VA research subjects in the Cleveland area. Specifically, should we have challenges recruiting Veterans, we will recruit from civilians with TBI with the help of Physical Medicine and Rehabilitation physicians at MetroHealth Medical Center, a local trauma center (See Letter of Support). In 2014, MetroHealth Medical Center had 166 inpatient TBI admissions: 101 had TBI as their sole disabling injury, 58 also had multiple fractures, and 5 also had spinal cord injuries. These statistics are typical of any given year at Metro Hospital. About half of the above patients will be followed in the outpatient clinic, some for a short time, and others chronically. About 250 chronic patients are seen sporadically about 1-4 times per year depending on their needs. A small fraction of this population have upper extremity weakness.
*According to VHA Handbook 1605.04 Notice of Privacy Practices VHA must provide a copy of its VHA Notice of Privacy Practices to all non-Veteran patients (e.g., active duty personnel or those seeking care in humanitarian circumstances) receiving care or treatment at a VHA health care facility or non-Veteran research subjects enrolled in an approved VHA research study with clinical trials. VA Form 10-0483 Acknowledgement of the Notice of Privacy Practices should be signed by the non-Veteran research subject at the time of consent and given a copy of the Notice of Privacy Practices. Once the Acknowledgement Form is signed please send a copy to the Privacy Officer. If additional information is needed please contact your Facility Privacy Officers [name] or [name] [contact] / [contact] [contact] / [contact].
25. Which vulnerable population(s) will be TARGETED for recruitment in this study:
• Indicate only those populations that are specifically targeted for the research described in this document.
• It is not necessary to check any box if, for example, your study will include a full range of subjects, some of whom may be elderly or subjects who might incidentally be employees.
N/A Chart Review (proceed to Item 30)
NONE (proceed to Item 26)
☐ Medical students, house staff, or Employees of the VAMC or Case
Pregnant Women OR Women who are Breastfeeding, Human Fetuses, or Neonates
☐ Children – Complete Section 14 "Children as Research Subjects"

Prisoners (The LSCDVAMC does not conduct research involving prisoners)

Persons with Cognitive, Social, Economic, or Educational Disadvantages (describe):

Persons with Acute/Severe Mental/Physical Disabilities (describe):

☐ Targeting Persons over Age 65

	Others (describe):
	a. Provide the $\underline{\text{Scientific}}$ and $\underline{\text{Ethical}}$ reasons for Targeting these vulnerable populations in the research:
	b. What additional safeguards or provisions will be used to protect the rights and welfare of the identified targeted vulnerable subjects?
	☐ Surrogate consent
	☐ Subject assent
	Use of a consent or Medical monitor
	Use of a waiting period
	☐ A patient advocate will participate in the informed consent process
	☐ Key elements of informed consent will be presented orally
	☐ No supervisor or rater will be involved in obtaining consent
	Other - Describe Additional safeguards you plan to use
	c. Describe the procedures used to ensure that the subject's legally authorized representative is well informed regarding his/her role and obligation to protect persons with impaired decision making capacity:
20.	Procedures for Recruiting Subjects -check all that apply and attach all recruitment materials:  ☐ Not Applicable  ☐ Materials; Recruitment Letter, Posting on Bulletin Board, Brochure, Flyer, Post card, etc.
	☐ Media; Internet Ads, Press Releases, Newspaper, Radio
	☐ Investigator's Patient Population
	□ Physician Referral
	☐ Letters to Physicians/Clinicians
	Other (describe): registry of study on clinicaltrials.gov or equivalent public study registry
27.	Will VA computer systems be used to identify potential subjects?
	• e.g. VISTA, CPRS, Pharmacy Databases, other clinical databases, etc,
	No Yes-Describe how the computer will be used to identify patients. List all systems d and all information to be collected: We will review medical records on CPRS during the eening process that pertains to medical history and medications.
28.	Will subjects be identified and/or recruited in clinics and/or inpatient wards at the LSDCVAMC?
	☐ No ☐ Yes- explicitly describe your process for identifying and/or recruiting these patients: (address all cohorts): a flier will be posted in clinical areas and information about the study will be disseminated by word of mouth to clinicians working with the study population.

29. In addition to the consent form will any other materials be given to the subject?

∐ N/A	Chart/data review
□ No	⊠ Yes- check all that apply and submit for IRB review:
	Letter
	☐ Information Sheets
	⊠ Questionnaire, Survey, Diary
	Other (flver, brochure, describe): Recruitment flvers

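### The MEP recruitment-curve area has no stated EMG normalisation, so it does not control for EMG recording variables; an M-wave-normalised FCR area should be added

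*Combined protocol and SAP*

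**What the plan says.** Item 13, under Single-pulse TMS-induced measures, builds the curve as follows: "The mean MEP peak-to-peak amplitude is plotted against SO creating the recruitment curve MEP-rc". The outcome is then defined: "The area under the MEP-rc curve is the cortical excitability outcome measure". Curves are taken from three muscles on both sides: "MEP-rc will be generated first dorsal interosseous muscle, extensor carpi radialis and flexor carpi radialis of the paretic and non-paretic upper limb". These muscles are abbreviated below as FDI, ECR and FCR.

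Two safeguards come with it. The range of stimuli is set for each subject and "held constant at each recording session to compensate for the more variable nature of the stroke-affected MEP response". On the EMG side, "The EMG electrodes positions will also be replicated between sessions". The paragraph closes with the claim at issue: "The area under MEP-rc captures the cortical excitability changes while controlling for TMS and EMG recording variables".

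Under Neuroplasticity measures, median nerve stimulation "will evoke a compound muscle potential (M wave in the flexor carpi radialis muscle) and an H wave". The only stated use of that M wave is in the H/M ratio. Table 2 marks TMS and H-reflex in the same four columns: week 1 (baseline) and weeks 9, 13 and 22. Item 10 plans to compare the TMS measures across those time points. Item 14 records no control group and no randomisation.

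**The concern.** The area is built from recorded EMG amplitude. If the amplitude of every response at one visit is scaled up or down for a reason unrelated to the brain, the area is scaled with it. Such reasons include skin impedance, electrode contact and the size of the muscle's own response. Nothing in the description divides that scale out, yet the plan says it is controlled.

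This matters more than usual because the comparison is single-arm and before-after. Nine weeks of therapy and training followed by nine weeks of home practice exercise the limb being recorded. A peripheral change over the study would coincide with the time effect under test, and a rise in area could be read as cortical plasticity when part of it arose in muscle or at the electrode. The plan schedules a peripheral reference signal for one of the three muscles in the same weeks, but does not use it for this purpose.

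**Working it through.** The documents give no computed figure for this outcome. The sample size of 11 in Item 11 belongs to the Fugl-Meyer paired t-test. It reproduces (power 0.961 at n = 11, d = 1.107, one-sided alpha 0.05), but nothing here depends on it.

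**Inputs.** Amplitude scale, area outcome, fixed stimulus range and replicated electrode positions: Item 13, MEP-rc. M wave in FCR: Item 13, H Reflex. Visits: Table 2. Between-visit variation in EMG gain: not given, so assumed below.

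**Step 1: how gain enters the area.** Let A be the area under MEP(s) over a subject's fixed range of stimulator output s. If a visit's recording multiplies all amplitudes by g, the area becomes g × A, and the apparent change is g − 1. A numerical check on an illustrative S-shaped curve gives:

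| g | change in raw area | normalised area relative to g = 1 |
|---|---|---|
| 0.8 | −20% | 1.00 |
| 0.9 | −10% | 1.00 |
| 1.1 | +10% | 1.00 |
| 1.2 | +20% | 1.00 |
| 1.3 | +30% | 1.00 |

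The last column divides each MEP by an M wave carrying the same g: (g × MEP)/(g × M) = MEP/M. It works only if both signals come from the same muscle through the same electrodes at the same visit. For recording gain the proportionality is exact. For a change in the muscle's peripheral response it is approximate.

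**Step 2: what the safeguards do.** Fixing the stimulus range keeps the limits of the area the same at every visit; it does not act on g. Replicating electrode positions narrows the spread of g but leaves impedance, contact and muscle changes.

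**Step 3: random variation.** Assume g is log-normal and independent between visits, with coefficient of variation CV. The SD of the log ratio of two visits is √2 × √ln(1 + CV²). The 95% range of apparent change in one participant with no true change is exp(±1.96 × SD) − 1:

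| assumed CV | SD of log ratio | 95% range |
|---|---|---|
| 5% | 0.071 | −13% to +15% |
| 10% | 0.141 | −24% to +32% |
| 20% | 0.280 | −42% to +73% |
| 30% | 0.415 | −56% to +126% |

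This part averages out across participants. At CV 10% and the full planned 20 subjects, the SD of the mean log ratio is 0.141/√20 = 0.0315. The range for the group's geometric mean is then exp(±1.96 × 0.0315) − 1, about −6% to +6%. The TMS safety exclusions and attrition would leave fewer than 20 and a wider range. A paired analysis already carries this scatter in its standard error, so it costs precision rather than creating a false rise.

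**Step 4: systematic change.** A shared change in peripheral response does not average out. If it were 10% (assumed), the group's raw area would rise by about 10% at any sample size.

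**Step 5: what can be normalised.** FCR has both an MEP curve and an M wave; FDI and ECR have no M wave. The plan does not state the side of the M wave, whether it is taken to its maximum, or whether its electrodes are those used for TMS.

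**The case against.** The case on the other side has real weight.

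- **Aim 1 does not rest on this area alone.** MRI does not use EMG amplitude. H/M is a ratio in which a common gain cancels. The onset and offset of the ipsilateral silent period are set against a threshold from pre-stimulus EMG, so gain largely cancels in its duration. The non-paretic curves are a partial within-subject comparator, though they do not share the paretic electrodes. A reader might infer that the neuroplastic part of Aim 1 is uninterpretable; the documents do not support that. These measures do not replace the recruitment curve, however: H/M is spinal, the silent period concerns transcallosal inhibition, and MRI stops at week 13.
- **Impedance and contact mostly add noise.** Nothing in the documents suggests that they drift upward. A reader might infer that electrode changes would produce a false group-level rise; that does not follow. Only a systematic peripheral change would bias the result, and the documents say nothing about its size.
- **The absence of normalisation is inferred from silence.** The area outcome carries a citation that may describe further processing. Still, the plan states its reference where it uses one (H/M, and pre-stimulus EMG for the silent period) and states none here.
- **The M wave covers one muscle of three.** Availability of a reference signal is no scientific reason to make FCR the leading muscle. That objection stands in full.
- **Limited weight in the trial.** The measure lies outside the Bonferroni-adjusted primary analyses, no sample-size figure depends on it, and it is collected only in participants who pass the TMS safety criteria.

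None of this rescues the statement that the area itself controls for EMG recording variables.

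**Conclusion.** The point holds in a limited form. As described, the area has no protection against a visit-level EMG scale factor beyond procedural care, and the sentence claiming control of EMG recording variables should not stand. Recording gain passes through exactly; peripheral muscle change passes through approximately. Without a control group, a rise in the raw area is not by itself evidence of cortical change.

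The actual size is unknown. The gains of 0.8 to 1.3 and the CVs of 5% to 30% are assumptions that show how the measure behaves; they do not estimate error in this trial. The conclusion rests on the algebra and on reading the unstated normalisation as absent. It concerns the interpretation of one neuroplasticity measure and leaves the primary analyses untouched.

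**What to change.** 1. Reword the closing sentence of the MEP-rc paragraph to say that EMG recording conditions are controlled by procedure only (replicated electrode positions, fixed stimulus range) and that the area remains sensitive to changes in recorded amplitude.
2. Add an FCR area in which each MEP is a percentage of the same-visit maximal FCR M wave. Use the limb in which the H-reflex is recorded and leave the same electrodes in place for both tests. State the side, and state that the M wave is taken to its plateau.
3. Report it alongside the raw FCR, FDI and ECR areas, without ranking FCR above the others.
4. Attribute an FCR change to cortical excitability only if it persists after normalisation. Describe FDI and ECR changes as changes in raw amplitude.

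The cost is small: analysis wording, running H-reflex and TMS with the FCR electrodes undisturbed in weeks 1, 9, 13 and 22, and a few more stimuli if the H/M protocol stops short of the M-wave plateau. Dividing by a measured M wave adds some noise, and FDI and ECR remain un-normalised.
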